6.3.2 Follow-up for toxicities

Patients whose treatment is interrupted or permanently discontinued due to an adverse event or clinically significant laboratory value, must be followed up at least once a week (or more frequently if required by institutional practices, or if clinically indicated) for 4 weeks, and subsequently at approximately 4-week intervals, until resolution or stabilization of the event, whichever comes first.

Appropriate clinical experts such as ophthalmologist, endocrinologist, dermatologist, psychiatrists etc. should be consulted as deemed necessary.

Table 6-9 outlines the follow-up evaluation recommended for toxicities of specific types and CTCAE grades.

Table 6-9 Follow-up evaluations for selected toxicities

TOXICITY	FOLLOW-UP EVALUATION
Blood and lymphatic system disorders	Test twice weekly until \leq CTCAE grade 1, then restart treatment. Continue to test weekly until resolution to baseline or stabilization.
Investigations (hematologic) Neutropenia \geq CTCAE grade 3 Thrombocytopenia \geq CTCAE grade 3	Test twice weekly until \leq CTCAE grade 1, then restart treatment. Continue to test weekly until resolution to baseline or stabilization. Perform physical exam for check on bruising in case of major thrombocytopenia.
Investigations (hepatic) Total bilirubin $\geq 2 \times$ ULN OR AST/ALT \geq CTCAE grade 3 ($> 5 \times$ ULN)	Test twice weekly until \leq CTCAE grade 1, (or \leq CTCAE grade 2 for ALT/AST if liver metastases are present) then restart treatment. Continue to test weekly until resolution to baseline or stabilization. Patients with total bilirubin $>$ ULN (any duration) should have fractionation of bilirubin into total/direct or indirect/direct components and any additional work-up as clinically indicated by these results. Follow-up of hyperbilirubinemia should proceed as per the guidelines above, irrespective of the results of fractionation.
Investigations (metabolic) Amylase or lipase \geq CTCAE grade 3	Test twice weekly until \leq CTCAE grade 2, then restart treatment. Continue to test weekly until resolution to \leq CTCAE grade 1 or stabilization. A CT scan or equivalent imaging procedure to assess the pancreas, liver, and gallbladder is recommended within 7 days of the first occurrence of any \geq

	CTCAE grade 3 result, to exclude disease progression or potential other liver disease. In patients with serum triglycerides \geq 500 mg/dL, urine amylase also needs to be tested.
Cardiac disorders ECG abnormalities indicative of ischemic event	Monitor toxicity until resolution to grade 1 or baseline. If applicable, monitor ECGs twice weekly until normalization or stabilization.
Investigations (creatinine) creatinine \geq CTCAE grade 3	If serum creatinine \geq CTCAE grade 3 has been demonstrated, this parameter must be repeated at least twice a week until resolution to \leq CTCAE grade 1 or baseline, and then at least weekly until either initiation of re-treatment or until stabilization. Patients will be instructed to increase hydration until resolution to \leq CTCAE grade 1 or baseline.
Ophthalmological disorders	Follow the advice of an ophthalmologist

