6.3 Dose modifications

6.3.1 Dose modification and dose delay

For patients who do not tolerate the protocol-specified dosing schedule, dose adjustments are permitted in order to allow the patient to continue the study treatment. The following guidelines need to be applied:

These changes must be recorded on the Dosage Administration Record CRF.

All dose modifications should be based on the worst preceding toxicity.

Each patient is only allowed 2 dose reductions as showed in [Table 6-7](#).

If a patient requires a dose interruption of > 14 days from the intended day of the next scheduled dose, then the patient must be discontinued from the study. Patients who discontinue the study for a study related adverse event or an abnormal laboratory value must be followed as described in [Table 6-](#).

Table 6-7 Dose adjustment of HH2710

	HH2710(mg)
Dose	Starting Dose
First dose reduction	75% of the starting dose*
Second dose reduction	50% of the starting dose*

* The actual reduced dose should take into account the drug specification

Adjust reference values in the table below according to the CTCAE V5.0 used in the study.

The criteria for interruption and re-initiation of HH2710 treatment is showed in [Table 6-](#)

Table 6-8 Criteria for interruption, re-initiation of HH2710 treatment and permanently discontinuation

Recommended dose modifications for HH2710	
Worst toxicity	Recommended dose modifications any time during a cycle of therapy, including intended day of dosing^b
CTCAE Grade^a (value)	
No toxicity	Maintain dose level
Investigations (Hematologic)	
Neutropenia (ANC)	
Grade 1 (ANC < LLN - 1500/mm ³)	Maintain dose level
Grade 2 (ANC < 1500 - 1000/mm ³)	Maintain dose level
Grade 3 (ANC < 1000 - 500/mm ³)	Discontinue HH2710: 
 - If elevation lasts for \leq 7 days: Resume treatment at same dose level - If elevation lasts for >7 days: Resume treatment at ≥ 1 dose level
Grade 4 (ANC < 500/mm ³)	Discontinue dose until resolved to \leq Grade 2, then ≥ 1 dose level 
If there is no recovery to \leq Grade 2 or there is recurrent grade 3 or 4 neutropenia, G-CSF/Neulasta may be given at physician discretion.
 
If no recovery to \leq Grade 2, permanently discontinue HH2710

Thrombocytopenia	
Grade 1 (PLT < LLN - 75,000/mm ³)	Maintain dose level
Grade 2 (PLT < 75,000 - 50,000/mm ³)	Maintain dose level

Recommended dose modifications for HH2710	

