Worst toxicity CTCAE Grade^a (value)	Recommended dose modifications any time during a cycle of therapy, including intended day of dosing^b
Grade 3 (PLT < 50,000 - 25,000/mm ³)	
Discontinue dose until resolved to \leq Grade 2, then:
 
 - If resolved in \leq 7 days, then maintain dose level - If resolved in $>$ 7 days, then \downarrow 1 dose level 
If no recovery to \leq Grade 2, permanently discontinue HH2710
 
Second occurrence: discontinue until toxicity resolves to \leq Grade 2, reduce to by another dose level.
 
3rd occurrence permanently discontinue HH2710.

Grade 4 (PLT < 25,000/mm ³)	
Discontinue dose until resolved to \leq Grade 2, then \downarrow 1 dose level
 
If no recovery to \leq Grade 2, permanently discontinue HH2710
 
Second occurrence: discontinue until toxicity resolves to \leq Grade 2, reduce to by another dose level.
 
3rd occurrence permanently discontinue HH2710.

Febrile neutropenia (ANC < 1.0 x 10 ⁹ /L, fever \geq 38.5°C)	Discontinue dose until resolved, then \downarrow 1 dose level
First episode	
Discontinue HH2710 until afebrile and ANC $>$ 1000.
 
Add Filgrastim/Neulasta per physician discretion.

Second episode	
Discontinue HH2710 until afebrile and ANC $>$ 1000.
 
Add Filgrastim/ Neulasta per treating physician discretion.
 
Restart HH2710 at dose reduced by one dose level and monitor as clinically.

Recommended dose modifications for HH2710	
Worst toxicity CTCAE Grade^a (value)	Recommended dose modifications any time during a cycle of therapy, including intended day of dosing^b
Third episode	Discontinue HH2710 until afebrile and ANC >1000. Add Filgrastim/ Neulasta per treating physician discretion. Restart HH2710 reduced by another dose level and monitor as clinically indicated.
Fourth episode	Permanently discontinue HH2710 and continue follow-up protocol.
Investigations (Hematologic) for LCH	Manage as per institutional standard or global guidance.
Investigations (Renal)	
Serum creatinine	
Grade 1 (> ULN - 1.5 x ULN)	Maintain dose level
Grade 2 (>1.5 - 3.0 x baseline; > 1.5 - 3.0 x ULN)	Discontinue dose until resolved to \leq Grade 1 or baseline, then maintain dose level
Grade 3 (>3.0 x baseline; > 3.0 - 6.0 x ULN)	Permanently discontinue HH2710
Grade 4 (> 6.0 x ULN)	Permanently discontinue HH2710
Investigations (Hepatic)*	
Bilirubin	

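### Protocol Tables 6-8 and 6-9 set restart thresholds one grade apart after Grade 4 neutropenia and Grade 3–4 thrombocytopenia

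*Protocol*

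**What the plan says.** Protocol section 6.3.1, Table 6-8, sets interruption, restart and permanent stopping by toxicity.

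- Grade 4 neutropenia: "Discontinue dose until resolved to \leq Grade 2", then restart one dose level lower.
- Grade 3 and Grade 4 thrombocytopenia: the first occurrence carries the same Grade 2 condition. The second reads "Second occurrence: discontinue until toxicity resolves to \leq Grade 2, reduce to by another dose level". A third is a permanent stop.
- Grade 3 neutropenia: the restart dose depends on whether the event lasted more than 7 days ("Resume treatment at same dose level" if it did not). No recovery grade is given.
- Serum creatinine, "Grade 3 (>3.0 x baseline; > 3.0 - 6.0 x ULN") and Grade 4: permanent discontinuation.
- Hematologic events in LCH: left to institutional standard or global guidance.

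Protocol section 6.3.2, Table 6-9, covers follow-up of selected toxicities. For neutropenia or thrombocytopenia of Grade 3 or higher it asks for twice-weekly tests until at or below "CTCAE grade 1, then restart treatment. Continue to test weekly until resolution to baseline or stabilization". For creatinine of Grade 3 or higher, testing runs at least twice a week until Grade 1 or baseline, "and then at least weekly until either initiation of re-treatment or until stabilization".

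Section 6.3.1 also requires discontinuation when an interruption exceeds 14 days from the intended day of the next dose.

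**The concern.** A site treating a recovering cytopenia finds two recovery grades at which to restart, in adjacent subsections of the same chapter, and no statement of which takes precedence. These are patient-safety instructions, and protocol section 1.2.2 lists hematological toxicity among the important potential risks.

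The restart grade also shapes the data. It affects how long dosing is held, and through the duration rules it can affect the restart dose and whether the patient stays on treatment. SAP section 8.6 summarizes reductions, interruptions and withdrawals with their reasons, and SAP section 8.8.1.1 summarizes adverse events leading to each. If sites followed different tables, part of the variation in those summaries would reflect the table used and not the drug. Safety and tolerability are the Phase I primary objective.

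**Working it through.** No statistical calculation applies. The check is a row-by-row comparison, followed by the grade limits printed in Table 6-8.

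**Step 1: the rows side by side**

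| Event | Table 6-8 | Table 6-9 | Relation |
|---|---|---|---|
| Neutropenia Grade 4 | restart at ≤ Grade 2 | restart at ≤ Grade 1 | one grade apart |
| Thrombocytopenia Grade 3–4, first or second occurrence | restart at ≤ Grade 2 | restart at ≤ Grade 1 | one grade apart |
| Thrombocytopenia Grade 3–4, third occurrence | permanent stop | occurrence not distinguished | no restart grade in Table 6-8 |
| Neutropenia Grade 3 | no recovery grade | restart at ≤ Grade 1 | gap, not two grades |
| Creatinine Grade 3–4 | permanent stop | test until re-treatment or stabilization | conflict only implied |
| AST/ALT Grade 3 | ≤ Grade 1, or ≤ Grade 2 with liver metastases | same | agree |
| Amylase/lipase Grade 3 | ≤ Grade 2 | ≤ Grade 2 | agree |

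The last two rows show that Table 6-9 does not apply one generic grade. Its thresholds vary by toxicity and match Table 6-8 there, so the cytopenia rows are a real mismatch.

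**Step 2: the band in dispute**

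The lower limits in Table 6-8 are:

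- Platelets: Grade 1 at 75,000/mm3, Grade 2 at 50,000/mm3. Band: 75,000 − 50,000 = 25,000/mm3.
- ANC: Grade 1 at 1,500/mm3, Grade 2 at 1,000/mm3. Band: 1,500 − 1,000 = 500/mm3.

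A count inside the band allows restart under Table 6-8 and not yet under Table 6-9. A count already at Grade 1 or better at the test that ends the hold meets both recovery thresholds.

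**Step 3: what follows from the difference**

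Let t2 be the day the count first reaches Grade 2 and t1 the day it first reaches Grade 1, so that t2 ≤ t1.

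- Interruption: it ends at t2 under one table and at t1 under the other. The difference is t1 − t2.
- Restart dose: Table 6-8 keeps the dose after Grade 3 thrombocytopenia if it resolves within 7 days and lowers it by one level otherwise. If a site counts the Table 6-9 grade as resolution, the dose differs when t2 ≤ 7 < t1. This applies to the first occurrence, because a second brings a reduction in any case. Grade 4 neutropenia and Grade 4 thrombocytopenia also bring a reduction whatever the duration.
- Discontinuation: with days counted from the intended next dose, the 14-day rule gives different outcomes when t2 ≤ 14 < t1.

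The documents give no recovery-time data, so the share of patients in either situation cannot be computed.

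**Step 4: creatinine**

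Table 6-9 gives two end points for testing. A patient stopped permanently under Table 6-8 can be followed to stabilization, so both tables can be obeyed. The mention of re-treatment has no use if the stop is permanent, but the row does not order a restart.

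**The case against.** The best defense is that the two tables have different jobs. Section 6.3.1 and the title of Table 6-8 present it as the criteria for interruption and restart, whereas section 6.3.2 introduces Table 6-9 as recommended follow-up evaluations. A careful site might therefore take the restart grade from Table 6-8. Footnote b to Table 6-8 also allows earlier resumption case by case after discussion with the sponsor.

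This makes divergent practice less likely but does not remove the contradiction. The Table 6-9 cytopenia rows contain an explicit restart instruction, and no sentence gives either table precedence. Footnote b is an exception to a threshold and does not say which threshold it departs from.

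Other objections stand and limit the point:

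- A reader might infer that sites will manage these events differently, or that every qualifying event is affected. The text supports only that they may differ. The dispute is confined to counts passing through the Grade 2 band, hematologic events in LCH follow institutional standard or global guidance under Table 6-8, and a third thrombocytopenia is a permanent stop there.
- A reader might treat Grade 3 neutropenia as a third mismatch. Table 6-8 states no recovery grade there, so it is a gap.
- A reader might call the creatinine rows a direct contradiction. The stabilization end point lets both be followed.
- Protocol section 1.2.2 says most hematological events so far were Grade 1 or 2 and that no significant nephrotoxicity was seen, so the number affected may be small.
- SAP section 7 says the program has been stopped, which limits what a correction can still change.

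**Conclusion.** The contradiction holds for Grade 4 neutropenia and for first or second occurrences of Grade 3–4 thrombocytopenia in patients without LCH. Its size is one CTCAE grade: platelets of 50,000 against 75,000/mm3, and ANC of 1,000 against 1,500/mm3. It can change the length of interruption, the restart dose after a first Grade 3 thrombocytopenia, and discontinuation under the 14-day rule. The dose effect assumes that a site carries the Table 6-9 grade into the 7-day rule. The number of patients affected is unknown.

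The creatinine wording is a lesser inconsistency, by implication only. With the program stopped, the practical effect is mainly on any patients still on treatment and on how the interruption, reduction and withdrawal summaries are read. No view is taken on which threshold is clinically right.

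**What to change.** Reconcile Tables 6-8 and 6-9 so that each cytopenia has one restart threshold, stated once and cross-referenced from the other table. Align the creatinine wording for Grade 3 or higher with a single instruction. The sponsor's clinical team decides which rule applies in each case.

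The same pass should check three neighboring places: the missing recovery grade for Grade 3 neutropenia; the febrile neutropenia condition ("Discontinue HH2710 until afebrile and ANC" above 1000, a level that includes Grade 2) against the blood and lymphatic row of Table 6-9; and the Table 6-9 rows worded for Grade 3 or higher, which also take in events that Table 6-8 stops permanently, such as Grade 4 AST/ALT and Grade 4 amylase or lipase.

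The cost is table wording and a notice to sites. Sample size, endpoints and planned analyses do not change. Given the early stop, the study report should also say that interruption data were collected while two restart thresholds were in print.

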6.3.3 Anticipated risks and safety concerns of the study drug

Overall, appropriate eligibility criteria and specific DLT definitions, as well as specific dose modification and stopping rules are included in this protocol. Recommended guidelines for prophylactic or supportive treatment for expected toxicities, including management of study-drug induced adverse events, i.e., skin toxicity and diarrhea are provided in IB. Refer to preclinical toxicity and or clinical data of other MAPK drugs found in the IB.

6.4 Concomitant medications

6.4.1 Permitted concomitant therapy

The patient must be told to notify the investigational site about any new medications he/she takes after the start of the study drug. All medications (other than study drug) and significant non-drug therapies (including physical therapy, herbal/natural medications and blood transfusions) administered during the study must be listed on the Concomitant Medications or the Procedures and Significant Non-Drug Therapies CRF.

6.4.2 Permitted concomitant therapy requiring caution and/or action

HH2710 inhibits CYP2C8, CYP2C9, CYP2C19, CYP3A4/5 (midazolam, as substrate) and CYP3A4/5 (testosterone, as substrate) *in vitro* with IC₅₀s of 4.37 μ M, 4.52 μ M, 8.75 μ M, 8.38 μ M, and 7.03 μ M. The drug-drug interaction potential of HH2710 due to inhibition of CYP2C8, CYP2C9, CYP2C19 and CYP3A4/5 is low based on its clinical exposure. Caution should be taken

when substrates of CYP2C8, CYP2C9, CYP2C19 and CYP3A4/5 are combined with HH2710, in particular those with a narrow therapeutic margin.

HH2710 induces CYP2B6 and CYP3A4 at 10 μ M *in vitro*. The drug-drug interaction potential of HH2710 due to induction of CYP2B6 and CYP3A4 is low based on its clinical exposure. Caution should be taken when sensitive substrates of CYP2B6 and CYP3A4 are combined with HH2710.

6.4.3 Prohibited concomitant therapy

Anticancer therapy (chemotherapy, biologic or radiation therapy, surgery or Chinese medicine/Chinese patent medicine with anti-tumor effect) other than the study treatments must not be given to patients while the patient is on the study. If such agents are required for a patient, then the patient must be discontinued from the study.

In vitro data indicate Drug HH2710 is metabolized primarily by CYP3A, therefore strong inhibitors of CYP3A4 (e.g., clarithromycin, itraconazole, ketoconazole, telithromycin, etc.) and strong CYP3A4 inducers (e.g., carbamazepine, rifampicin, St. John's wort, etc.) should be avoided. Gastric acid reducing agents and sensitive substrates of CYP2C8, CYP2C9, and CYP2C19 also should be avoided. Refer to [**Appendix 14.7**](#) for a list of prohibited medications. This list may not be comprehensive.

Current treatment with agents including vitamins, supplements, and herbal supplements that are metabolized solely through CYP3A4 should be prohibited.

In vitro data indicate HH2710 is a potential P-gp substrate. Strong P-gp inhibitor will likely increase the exposure level of HH2710. Strong P-gp inhibitor should be avoided (Refer to [**Appendix 14.8**](#)).

6.5 Patient numbering, treatment assignment or randomization

6.5.1 Patient numbering

Each patient is identified in the study by a Patient Number (Patient No.), that is assigned when the patient is first enrolled for screening and is retained as the primary identifier for the patient throughout his/her entire participation in the study. The Patient No. consists of the Site Number (Site No.) (As assigned by Haihe to the investigative site) with a sequential patient number suffixed to it, so that each patient is numbered uniquely across the entire database. Upon signing the informed consent form, the patient is assigned to the next sequential Patient No. available to the investigator through the iMedidata electronic data collection (EDC) interface.

6.5.2 Treatment assignment or randomization

No randomization is needed in this study. The treatment assignment is decided by the investigator.

6.5.3 Treatment blinding

Not applicable. This is an open-label study.

6.6 Study drug preparation and dispensation

The investigator or responsible site personnel must instruct the patient or caregiver to take the study drugs as per protocol. Study drug(s) HH2710 will be dispensed to the patient by authorized site personnel only. All dosages prescribed to the patient and all dose changes during the study must be recorded on the Dosage Administration Record CRF.

Table 6-8 Preparation and dispensing

Study treatments	Dispensing	Preparation
HH2710	
Capsules including instructions for administration are dispensed by study personnel on an outpatient basis.
 
Patients will be provided with adequate supply of study treatment for self-administration at home until at least their next scheduled study visit.
	Not applicable

6.6.1 Study drug packaging and labeling

The study medication packaging has a 2-part label. A unique medication number is printed on each part of this label which corresponds to one of the treatment arms and a [specific visit or dose/dose level]. Responsible site personnel will identify the study treatment package(s) to dispense to the patient according to the designed dosage. Site personnel will add the patient number on the label. Immediately before dispensing the package to the patient, site personnel will detach the outer part of the label from the packaging and affix it to the source document (Drug Label Form) for that patient's unique patient number.

Medication labels will be in the local language and comply with the legal requirements of each country. They will include storage conditions for the drug and the medication number but no information about the patient.

The packaging of study drug HH2710 is capsule in bottle.

The HH2710 capsules will be provided in an open-labeled packaging with space to enter the patient's identification number. The label will also include name/drug code and quantity of HH2710, clinical protocol number, batch number, administration instructions, storage instructions, and expiry date.

The contents of the label will be in accordance with all applicable regulatory requirements.

6.6.2 Drug supply and storage

Study drug HH2710 will be centrally supplied by Haihe. Study drug must be received by designated personnel at the study site, handled and stored safely and properly, and kept in a secured location to which only the investigator and designated site personnel have access. Upon receipt, the study drug should be stored according to the instructions specified on the drug labels and in the IB.

6.6.3 Study drug compliance and accountability

6.6.3.1 Study drug compliance

Compliance will be assessed by the investigator and/or study personnel at each patient visit and information provided by the patient and/or caregiver will be captured in the Drug Accountability Form. This information must be captured in the source document at each patient visit.

6.6.3.2 Study drug accountability

The investigator or designee must maintain an accurate record of the shipment and dispensing of study drug in a drug accountability log. Drug accountability will be noted by the field monitor during site visits and at the completion of the study. Patients will be asked to return all unused study drug and packaging on a regular basis, at the end of the study or at the time of study drug discontinuation.

At study close-out, and, as appropriate during the course of the study, the investigator will return all used and unused study treatment, packaging, drug labels, and a copy of the completed drug accountability log to the Haihe monitor or to the Haihe address provided in the investigator folder at each site.

